6.0 Multi-Site Research

6.1 Study Team:

DFCI will serve as the lead site for PediCARE and the single IRB of record for this small, pilot feasibility intervention study. The Study Team at each site will participate in monthly study phone calls to address (a) accrual rate, (b) study eligibility determination issues, (c) data completion rates including conformance with informed consent requirements, (d) intervention fidelity indicators, (e) adverse events, and (f) compliance with data management procedures.

6.2 Collaborating Sites and Role of Sites in Performing Proposed Research:

This study will be conducted at both DFCI and University of Alabama Birmingham Children's of Alabama (UAB). Inclusion of UAB as a collaborating site in this pilot study will leverage patient catchment areas which include both New England and Southern states to recruit a more diverse patient population from the perspective of race, ethnicity, geography and culture—particularly meaningful in the context of poverty as a social determinant of health. Furthermore, pilot feasibility at diverse sites will inform subsequent scalability of our approach for a multi-center RCT intervention study to definitively evaluate the impact of PediCARE on childhood cancer outcomes.

Under the direction of the site PI [name], UAB will recruit and enroll a total of 12 participants in study. Participants will be randomized to receipt of PediCARE or UC. UAB will maintain a local

patient tracking database, communicate participant enrollment data to DFCI for central administration of randomization and intervention components; administer baseline and follow-up parent surveys; and transmit required source documentation to DFCI for central data monitoring.

7.0 Study Timelines

New patients at each site are continuously identified by study teams. Eligible parents will be approached sequentially by study teams and offered an opportunity to participate following written informed consent. Participants who choose to enroll will be on study for 6-months.

8.0 Study Endpoints

8.1 Feasibility: The primary endpoint of this study is feasibility. Feasibility will be defined as at least 75% consent to randomization and at most 20% attrition per arm. We will assess process barriers to feasibility including recruitment, attrition by arm and parent report of PediCARE component utilization (i.e. food and transportation).

[figure not shown]
Study Timeline (Months)	Months 1 -6 Year 1	Months 7- 12 Year 1	Months 1-6 Year 2
Screen and enroll families (6 months)			
Intervention administration (6 months)			
Data analysis			

8.2 HMM and Utilization: The secondary endpoints of this study will be used to generate effect size estimates to support planning of a subsequent RCT. Secondary endpoints will be evaluated comparing recipients of PediCARE versus Usual Care. Secondary outcomes include change in HMM utilizing an HMM score (range 0-4) at 6-months compared to baseline; and proportion of patients experiencing an Emergency Department (ED) visit or Intensive Care Unit (ICU) admission over 6-months.

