4.0 Planned Enrollment

This study aims to enroll a total of 40 participants as follows:

Pilot RCT DFCI and UAB: The target sample size is 40 participants. At DFCI, a total of 28 participants will be enrolled and randomized (thus 14 participants will receive PediCARE and 14 participants will receive UC). At UAB a total of 12 participants will be enrolled and randomized (thus 6 participants will receive PediCARE and 6 participants will receive UC).

Families will be recruited consecutively at each site over a 6-month time period. Patients will be randomized 1:1 to PediCARE versus Usual Care (UC) and randomization will be stratified by site.

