11.0 Statistical Considerations

Accrual: Annually, 420 new patients receive chemotherapy at DFCI and 120 at UAB. Based on prior institutional HMH data, we estimate 20% will be eligible to participate at DFCI (N=84) and 30% will be eligible to participate at UAB (N=36). We estimate a 75% consent rate for a total possible annual sample size of N=90 patients (63 DFCI, 27 UAB). Forty patients will be accrued over 6-months at DFCI (n=28) and UAB (n=12). Patients will be randomized 1:1 by site to PediCARE versus UC.

Analysis Plan: Sample demographic, disease, treatment and utilization variables from the survey instruments and medical chart will be described by summary statistics.

The rate of consent to randomized intervention and the 6-month completion will be estimated along with a 90% confidence interval (CI). Feasibility will be established if the upper bound of the CI contains 75% and 80% for consent and follow-up respectively. With an estimated 60 eligible patients at 6 months, at least 39 (65%; 90% CI 53.6-75.2%) need to enroll for the upper bound of the 90% CI contain 75%. With an estimated 40 randomized patients, at least 28 (70%; 90% CI 56.0-81.7%) need to have complete 6-month data to have the upper bound of the 90% CI contain 80%. The 6-month completion rate will also be estimated along with a 90% CI by randomized arm (PediCARE and UC).

For each family, the difference between 6-month and baseline HMH scores will be categorized as improved (change score <0) or not improved (change score ≥0). For each arm, the proportion of families with improved HMH at the completion of the intervention (6-months) will be estimated along with a 90% exact CI. Based on prior data, we assume a 30% resolution in HMH in UC, thus the 90% CI will be within ±24.9%. For each arm, the per patient number of ED visits and ICU stays will be summarized (median, range). The proportion of patients with at least one ED and/or ICU visit will be estimated for each arm, as well as the difference between arms, along with a 90% confidence interval. Additionally, the rate of HMH at the completion of the intervention pilot (6-months) along with a 90% exact confidence will be estimated for UC and PediCARE. For the PediCARE arm, the cost per patient, study team contact hours, and proportion with successful receipt of all intervention components will be described overall and by site.

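### The HMH effect size makes no use of the baseline HMH score; adjusting for it would cost almost nothing, guard against chance imbalance and give a modest gain in precision.

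*Combined protocol and SAP*

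**What the plan says.** Section 8.2 (which types HMM for HMH) names the outcome: "Secondary outcomes include change in HMM utilizing an HMM score (range 0-4) at 6-months compared to baseline". It says the secondary endpoints compare PediCARE with usual care, and gives their purpose: "The secondary endpoints of this study will be used to generate effect size estimates to support planning of a subsequent RCT".

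Section 11 sets out the analysis. For each family, "the difference between 6-month and baseline HMH scores will be categorized as improved (change score <0) or not improved (change score ≥0"). Then, per arm, "the proportion of families with improved HMH at the completion of the intervention (6-months) will be estimated along with a 90% exact CI". The 6-month rate of HMH is also given per arm with an exact 90% interval. A contrast between arms is written for emergency and intensive care use ("The proportion of patients with at least one ED and/or ICU visit will be estimated for each arm, as well as the difference between arms"), but none is written for HMH.

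Section 4.0 states that "randomization will be stratified by site", and no other factor is named. Section 9.1.2 places randomization after the baseline survey, so every randomized family should have a baseline HMH score. No section uses that score as a covariate, a stratum or a standardization weight.

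**The concern.** Taking a change, or the sign of a change, does not remove dependence on the starting value. Under the Section 11 definition, a family that scores 0 on the baseline survey cannot improve and a family that scores 4 cannot worsen. Between those ends, a family with several hardships may have more ways to lose one than a family with a single hardship. If so, an arm that happens to start with higher scores will show more improvement whatever the intervention does.

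Randomization does not balance the score by design, and two groups of about 20 will differ on it by chance. The HMH effect size is meant to inform the planning of the next trial, and this pilot supplies only one randomization. A shift caused by imbalance in that one allocation would pass into the planning figure unnoticed, although the variable needed to correct it is already in the database.

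**Working it through.** **Inputs from the documents.** 40 families, 1:1, so 20 per arm (Section 4.0); HMH score 0-4; 'improved' means change below 0; 30% assumed for usual care (Section 11). The documents give no baseline score distribution and no rates at which domains resolve or appear. All such values below are assumptions, and a range is shown.

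**1. The plan's own precision figure.** Section 11 says "we assume a 30% resolution in HMH in UC, thus the 90% CI will be within ±24.9"%.
- One arm, 6/20, exact 90% interval: 14.0% to 50.8%, or -16.0/+20.8 points. This is not 24.9.
- Difference between arms, 20 per arm, 30% versus 50%: 1.645 × √(0.3×0.7/20 + 0.5×0.5/20) = 1.645 × √0.0230 = 24.9 points. This matches, although the 50% for PediCARE is an inference.
- Difference at 30% versus 30%: 1.645 × √(2×0.21/20) = 23.8 points.

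So a between-arm HMH contrast has a 90% half-width of about 24 points.

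**2. Does baseline affect the chance of improving?** Suppose each present domain resolves with probability 0.3 and each absent one appears with probability 0.1, independently and at every score. 'Improved' then means more domains resolved than appeared:
- Score 1: 0.3 × 0.9³ = 0.22
- Score 2: 0.42 × 0.81 + 0.09 × 0.99 = 0.43
- Score 3: 0.441 × 0.9 + 0.189 + 0.027 = 0.61
- Score 4: 1 - 0.7⁴ = 0.76

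The gradient comes from the constant-rate assumption. If persistence per domain rises with the score (0.65, 0.78, 0.85, 0.90), the chances are 0.25, 0.32, 0.36 and 0.34, which is nearly flat.

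**3. How large is chance imbalance?** With baseline scores 1/2/3/4 in 45/30/17/8% of families, the mean is 1.88 and the variance 4.46 - 1.88² = 0.926. The SD of the difference in arm means is √(2 × 0.926/20) = 0.30 points (0.24-0.35 across assumed distributions). A gap of 0.5 points or more occurs in about 11% of trials (5-18%).

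**4. How far does the crude contrast move?** With constant rates, each 1-point gap moves the difference in proportion improved by about 16 points (8-21), so a 0.5-point gap moves it by about 8 (4-11). As a second view, take baseline 50/30/15/5%, resolution 0.3 or 0.5, appearance 0.1 or 0.2, and no true effect. PediCARE starts at least 0.3 points higher in about 16% of simulated pilots. Its average lead at baseline is then about 0.42 points, and the slopes run from about 0.19 to 0.25. The false advantage is thus 0.42 × 0.19 = 8 points to 0.42 × 0.25 = 10.5 points; repeat simulations gave about 8-12. After linear adjustment for baseline it is near 0.

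**5. What does adjustment do to precision?** Simulated standard errors of the difference in proportion improved, 20 per arm, adjusting for baseline score only:

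| Assumed scenario | P(improved) by score | Crude | Adjusted | Ratio |
|---|---|---|---|---|
| Constant persistence 0.77 (about 30% improve) | 0.17, 0.34, 0.50, 0.65 (scores 1-4) | 0.148 | 0.141 | 1.05 |
| Constant persistence 0.60 | 0.29, 0.55, 0.74, 0.87 (1-4) | 0.158 | 0.147 | 1.08 |
| Constant persistence 0.70, 15% score 0 at baseline | 0, 0.22, 0.43, 0.61, 0.76 (0-4) | 0.149 | 0.135 | 1.11 |
| Harder to clear at higher scores | 0.25, 0.32, 0.36, 0.34 (1-4) | 0.143 | 0.144 | 0.99 |
| Much harder at higher scores | 0.34, 0.33, 0.31, 0.28 (1-4) | 0.151 | 0.153 | 0.99 |

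Constant-rate scenarios with every baseline score at least 1 give ratios of about 1.02-1.08. In the first row the 90% half-width falls from 1.645 × 0.148 = 24.3 to 1.645 × 0.141 = 23.2 points.

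**The case against.** The strongest reply is that this is a refinement and not an error. Feasibility is the primary endpoint, HMH is secondary, and no test is planned. Randomization keeps the crude contrast unbiased, its 90% interval covers correctly, and a narrowing of about one point is small in a 40-family pilot. All of that stands.

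Two stronger readings are tempting, and the documents support neither. A reader might infer that the baseline score largely determines who improves. The only structural facts concern scores of 0 and 4; the rest depends on rates that are not given. Under constant rates baseline explains about 12-21% of the variance of 'improved', and under 1% if higher scores are harder to clear. A reader might also take the larger gains that ANCOVA shows over a mean-change comparison as the size of the problem. Section 11 writes no mean-change contrast, so those gains do not describe the planned analysis.

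It is fair, too, to say that the plan lacks the HMH contrast itself, so there is strictly nothing yet to adjust. That does not remove the point: the estimate has to be written if Section 8.2 is to deliver an effect size, and it can be written with adjustment from the start.

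Finally, tabulating 'improved' by baseline score would leave about 10, 6 and 4 families per arm at scores 1, 2 and 3 or more (20 × 50%, 30% and 20% under the second assumed distribution), before dropout. Those cells are too small for a main result.

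**Conclusion.** The point holds as a low-cost improvement. The plan leaves unused a baseline measure that is collected before randomization and bears directly on its HMH outcome. In the single pilot to be run, chance imbalance could shift the crude difference in proportion improved by about 8-12 points when PediCARE starts at least 0.3 points higher, with a shift the other way when it starts lower. That is well inside the half-width of about 24 points, but large beside the differences a planner would want to tell apart. It rests on assumed constant per-domain rates; if higher scores are harder to clear, the shift largely disappears.

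The gain in standard error is about 2-10%, at the upper end if some families score 0 on the baseline survey. That is possible because Section 3.1 lets site providers do the eligibility screen separately from the survey. In the unfavourable scenarios adjustment costs about 1%. The crude analysis is neither biased on average nor invalid in coverage.

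**What to change.** In Section 11, with a matching line in 8.2:

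- Add a PediCARE minus usual care HMH estimate with a 90% CI, adjusted for baseline HMH score and site. Choose one form in advance: a linear model for the 6-month score, or a difference in proportion improved standardized to the pooled baseline distribution.
- Keep the crude per-arm proportions with exact intervals as description.
- Tabulate baseline HMH score by arm, including any scores of 0.
- Do not present 'improved' by baseline stratum as a main result.

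The cost is a few sentences and, in the linear model, one degree of freedom for baseline score and one for site, out of about 40 families. No new data are needed. Fixing the form now also prevents a later choice between crude and adjusted results.

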9.0 Study Procedures

Study Schema

9.1 Overall Study Design

PediCARE is a poverty-targeted intervention utilizing direct resource provision of groceries and transportation. We will pilot PediCARE in a randomized fashion in 40 newly diagnosed families with HMH at DFCI (N=28) and UAB (N=12) to assess feasibility and preliminary change in HMH and care utilization. Human subject participation includes:

- 1) Parent-completed baseline and post-intervention survey;
- 2) Randomized receipt of PediCARE versus UC over 6-months;
- 3) Medical record abstraction of child's chart.

9.1.2 Study Processes:

- Newly diagnosed families continuously screened for study eligibility; eligible families approached to offer consent consecutively (as detailed in section 5.1 Recruitment)
- All parents will complete the baseline HMH survey with the study CRA at time of enrollment. For those parents for whom in-person survey administration is infeasible, baseline surveys will be conducted by telephone, by virtual/video platforms, or by a hard-copy given to the parent to complete on their own and return to the study team.
- Post-survey completion, parents will be randomized to receipt of PediCARE or UC as detailed in Section 9.2. Parents randomized to PediCARE will be introduced to the food and transportation resource provisions by the site CRA (see section 9.3.2).
- Parents will receive the PediCARE intervention or Usual Care (UC) for a total of 6-months.
- Parents will complete a post-intervention survey at 6-months. All parents will be contacted by email or telephone (per family preference) in the weeks prior to the 6-month follow-up survey. Parents will then complete the 6-month follow-up survey with the study CRA. For those parents for whom in-person survey administration is infeasible, follow-up surveys will be conducted by telephone, by virtual/video platforms, or by a hard-copy given to the parent to complete on their own and return to the study team.
- Medical record abstraction performed at 6-months.
Enrolled parents will receive a total of \$100 in Amazon gift cards over the 6-months of study participation (\$50 gift card after baseline survey and \$50 gift card after post-intervention follow-up survey) to off-set the burden of their time.

9.1.3 Study Measures

HMH Survey Administration: Parents will complete the baseline HMH survey at time of enrollment; parents will complete the abbreviated follow-up HMH survey at intervention completion (6-months). The HMH survey constitutes an abbreviated version of the Oncology EIS survey which has been utilized in two prior studies with high willingness to participate and low participant burden.^{10,17} Survey domains include: 1) Sociodemographics; 2) HMH (housing, transportation, utilities, food); 3) Finances; 4) Current resources; 5) Social supports; 5) Resilience; and 6) Anxiety. Survey administration takes approximately 10-15 minutes and may be conducted with an interpreter. Surveys are preferentially administered face-to-face (questions read-aloud by CRA) to overcome health literacy barriers which are of particular pertinence in the target patient population for this study. Surveys may be administered either on an iPad or paper/pencil. For two-parent households, while one parent consents to study participation and serves as the primary survey respondent (e.g. demographics) it is permissible for both parents to contribute information to questions on household material hardship and finances per family preference. All families will be contacted by email or telephone (per family preference) in the week prior to the 6-month follow-up survey to remind them of the upcoming survey time-point. Families will then complete the 6-month follow-up survey with the study CRA either in clinic or inpatient. For those families for whom in-person survey administration is infeasible surveys may be conducted by telephone, virtual platform, or self-completed hardcopy as needed.

Medical Record Abstraction: Child demographic and clinical data will be collected via systematic chart review by trained CRAs at the completion of study receipt (6-months) and entered into a REDCap database. Ten percent of records will be abstracted by a second CRA and discrepancies will be reviewed to clarify abstraction methods and adjudicated by the PI and site PI. Abstracted data elements will include but not be limited to age, diagnosis, cancer risk group or stage, treatment protocol, treatment elements (chemotherapy, surgery, radiation), hospital lengths of stay, emergency department visits and ICU stays during intervention.

9.2 Procedures for Assignment to Study Group:

Enrolled participants will be randomized 1:1 by site to receive either the PediCARE intervention or UC for a duration of 6-months.

Participants will be randomly assigned to PediCARE or UC with a 1:1 allocation by site as per a computer-generated randomization sequence created by the study statistician. Sequences will be embedded in REDCap by informatics personnel. This approach to randomization will allow for real-time randomization of participants. Study personnel will not have access to the sequences. After randomization, participants and study team will be unblinded to group assignment as the intervention is not amenable to blinding.

9.3 Intervention Procedures:

The PediCARE study will pilot direct resource provision (groceries and transportation) to households of children newly diagnosed with cancer with a goal of reducing a concrete measure of poverty, household material hardship (HMH).

9.3.1 Usual Care (UC) Components (Control): UC psychosocial support in pediatric cancer is institution-specific but routinely includes (1) a psychosocial clinician available as part of the cancer care team; (2) social work screening for social and financial needs including such examples as insurance coverage and eligibility for Institutional, community or private cancer foundation supports; (3) social work assistance with applications on a case by case basis for insurance (i.e. Medicaid) and community/institutional/private financial supports; and (4) provision of parking vouchers and/or limited gift cards (e.g. cafeteria and hospital-retail food) when available.

9.3.2 PediCARE Intervention Components: PediCARE includes direct resource provision in two domains: Food and Transportation. Resource provision will be centrally administered by DFCI.

(1) **Food:** Families will receive a monthly pre-paid allocation of Instacart funds for grocery purchasing and delivery in a dollar amount adapted from the March 2018 U.S. Department of Agriculture's (USDA) Thrifty Food Plan (see Appendix B) for family size (e.g. family of 4 with two toddlers will receive \$640; cost range based on family sizes of 2-7 people and capped at 7 people). The Thrifty USDA Food Plan serves as the national standard for a nutritious diet at a minimal cost and is used as the basis for maximum SNAP benefit (e.g. food stamp) allotments, as such it represents a valid bench-mark for household food costs.

- At study entry, the site CRA will assist families randomized to PediCARE in creation of an Instacart account for online grocery purchasing and delivery. Account creation requires

a name, email address, telephone number, home address for grocery delivery, and a credit card, debit card, or gift card

- Families will subsequently be provided a monthly pre-paid allocation of Instacart funds the beginning of each month of study participation. Families will choose and order groceries at their discretion over the course of the study.
- Other logistics: Instacart grocery ordering can be performed on any smartphone or computer with internet access. Any enrolled family without access to either a smartphone or computer will be provided with access to an iPad in clinic or while inpatient for ordering. Groceries can be ordered for same-day or future delivery. Families who live in ZIP codes where Instacart delivery is not available (approximately 15% of the U.S.) will be provided with an equivalent dollar amount grocery gift card to their local grocery store.

(2) Transportation: Families will be provided with the option of either 48 round-trip rides (96 legs) over the course of six months to use as needed each month using RideHealth or (b) gas cards and parking passes to support an estimated 8 clinic/hospital visits per month. The flexibility of choosing which direct transportation support will best facilitate a family's ability to bring their child to clinic or the hospital is based on qualitative parent feedback from the PediCARE pretest.

(a) Transportation will be provided via RideHealth, a company which provides a HIPAA-compliant digital platform to coordinate patient transportation utilizing Uber/Lyft and other commercial ride services, a web-based on-demand transportation platform. This platform allows for HIPAA-compliant account generation using PHI on the back-end, and then links to ride-scheduling with Uber/Lyft or other commercial drivers on the front-end without PHI. Built for healthcare, RideHealth allows ride-authorization for patients between specified sites (i.e. home and hospital/clinic). Rides are booked by the parent, and can be booked in advance (e.g. for a planned clinic visit or hospital stay) or on-demand 24-hours a day via their website or dedicated call center (e.g. for unplanned clinic or Emergency Department visits). RideHealth provides real-time analytics on utilization and performance including timeliness and cost.

- At study entry, the lead-site CRA will create a RideHealth account for families randomized to PediCARE within the central DFCI RideHealth account. Families can view only their own information to facilitate ride requests. Each account will include pre-authorization for 48 round-trip rides (96 legs) over six months.
- The local site CRA will educate families on utilization of the RideHealth patient-facing app to request rides (process is similar to Uber/Lyft app for ride scheduling)
- Ride data including utilization, cost, and time will be provided to the lead site linked to study ID by RideHealth

(b) Families will be provided with gas cards in a dollar amount stratified by distance from hospital based on estimated average frequency of clinic visits/hospitalization and 2018 gas costs. Specifically, families who live <180 miles from the hospital will be provided with \$200/month in gas cards; those who live \geq 180 miles from the hospital will be provided with \$300/month in gas cards. Families will receive 8 parking passes per month at sites where families pay for parking.

PediCARE will provide both groceries and transportation support to all intervention recipients for the duration of the study. Pilot families will be randomized 1:1 at each site to receive the

PediCARE intervention or UC for 6-months which represents the most intensive phase of treatment for children with leukemia and neuroblastoma and covers the duration of chemotherapy treatment for most solid tumor and lymphoma diagnoses.

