2.0 Objectives

2.1 Overall Study Objectives:

The overarching goal of this study is to pilot a randomized controlled trial (RCT) of the Pediatric Cancer Resource Equity (PediCARE) intervention to determine feasibility of intervention administration in a childhood cancer population. Secondary goals include generation of effect size estimates for a primary endpoint of reduction in household material hardship (HMH) and a secondary endpoint of Emergency Department and Intensive Care Unit utilization to support

planning of a subsequent definitive multi-center RCT. PediCARE is a poverty-targeted intervention utilizing direct resource provision of groceries and transportation.

2.2 Specific Aims:

Pilot RCT to determine feasibility

To conduct a pilot RCT of the PediCARE intervention in 40 newly diagnosed pediatric cancer families with HMH at DFCI and UAB. Families in the intervention arm will receive PediCARE for 6-months. The control group will receive usual care. Data will be collected by parent survey at baseline and 6-months. The primary outcome will be defined as feasibility. Secondary outcomes will include improvement in HMH scores (range 0-4) at 6-months compared to baseline and Emergency Department (ED) and Intensive Care Unit (ICU) admissions. Analyses will focus on effect size estimates to plan a subsequent RCT.

H2a. Feasibility will be demonstrated by recruitment rate of 75% and follow-up survey data collection of 80% per arm.

H2b: There will be a trend towards a reduction in HMH scores (primary endpoint) and lower proportion of patients experiencing an ED visit or ICU admission over 6-months in the PediCARE versus usual care group.

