3.0 Inclusion and Exclusion Criteria

Children diagnosed with cancer at DFCI and UAB will serve as the study cohort for PediCARE with parents/guardians as survey informants and intervention recipients.

3.1 Inclusion criteria:

- 1) Child initiated chemotherapy in the last 2 months for newly diagnosed cancer;
- 2) Planned receipt of at least 4 cycles of chemotherapy at DFCI or UAB;
- 3) Parent/guardian screened positive for HMH*;
- 4) Child is <18 years at time of enrollment

* In accordance with previous research^{15-17,21,42} families will be operationalized as having HMH for eligibility purposes if they report at least one of the below four concrete needs: (1) Food insecurity.^{47,39,48} (2) Housing Insecurity.^{16,17} (3) Energy Insecurity.^{16,17} (4) Transportation Insecurity. Families are considered to have insecurity in a domain if they screen positive to at least one item. HMH screening is performed as standard of care by site-specific providers or will be conducted by a member of the research study team.

3.2 Exclusion criteria:

- 1) Child with diagnosis of relapsed cancer;
- 2) Child planned to receive fewer than 4 cycles of chemotherapy
- 3) Child planned to receive observation, radiation or surgical resection only;
- 4) Planned transfer of child to a non-DFCI or UAB facility for chemotherapy treatment;
- 5) Foreign national family receiving cancer care as an Embassy-pay patient;
- 6) Child is enrolled on DFCI 16-001 (due to ongoing embedded descriptive HMH study) or NA if enrolling at UAB

- 7) Child is enrolled on ANBL1531 or AALL1731 (due to ongoing embedded descriptive HMH studies)

3.3 Inclusion of Women and Minorities:

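### The ED/ICU endpoint counts scheduled and unscheduled ICU stays alike; any scheduled stays that PediCARE cannot affect would shrink the effect estimate meant for planning the next trial

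*Combined protocol and SAP*

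**What the plan says.** H2b (Section 2.2) predicts a "lower proportion of patients experiencing an ED visit or ICU admission over 6-months in the PediCARE versus usual care group", so fewer children with an event is read as benefit. Section 8.2 defines the endpoint as the "proportion of patients experiencing an Emergency Department (ED) visit or Intensive Care Unit (ICU) admission over 6-months" and says that the secondary endpoints are there to give effect sizes for planning a later RCT. Section 11.0 carries this into the analysis: "The proportion of patients with at least one ED and/or ICU visit will be estimated for each arm". The contrast between arms is to be reported too, with a 90% interval. Section 11.0 also summarises the number of ED visits and ICU stays per patient. No test, expected rate or power is stated for this endpoint.

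The data come from chart review at 6 months. Section 9.1.3 names "hospital lengths of stay, emergency department visits and ICU stays during intervention", along with diagnosis, treatment protocol and treatment elements that include surgery. The list is introduced as not exhaustive. It names no item for the reason for an ICU stay or for whether it was planned.

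On eligibility, Section 3.2 removes a "Child planned to receive observation, radiation or surgical resection only". A child who has chemotherapy and also surgery stays in the cohort.

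**The concern.** An ICU stay scheduled as part of the treatment plan, for example after planned surgery, is not something that groceries or transport could prevent. Under the present definition it makes the child an event in either arm. Such events do not favour one arm on average. They raise the event proportion in both arms and pull the difference toward zero.

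What is at stake is the planning estimate. The next trial would inherit a base rate that is too high and a difference that is too small for the utilization PediCARE could plausibly change. The confidence interval gives no sign of this, and repeating the definition in a larger trial would reproduce it.

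**Working it through.** **Inputs from the documents.** Total N is 40, randomized 1:1, so 20 per arm (Section 4.0). The event is any ED visit or ICU admission over 6 months (Sections 8.2 and 11.0). The interval is 90% (Section 11.0). The plan states no figure for this endpoint, so there is none to reproduce.

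**Assumptions, none of them in the documents.** The risk of an ED visit or unscheduled ICU stay is p0 = 50% under usual care and p1 = 35% under PediCARE. A fraction q of children has a scheduled ICU stay. This fraction is equal in both arms and independent of other events, with q taken as 0, 10%, 20% and 30%.

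**Step 1: observed risk.** A child is an event unless free of both kinds: 1 − (1 − p)(1 − q) = p + (1 − p)q.

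**Step 2: observed difference.** Subtracting the arms gives (p0 − p1)(1 − q). This already allows for children who would have been events anyway.

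**Step 3: pilot precision.** The 90% Wald half-width is 1.645 × √[a(1 − a)/20 + b(1 − b)/20], where a and b are the observed risks. At q = 0 this is 1.645 × √[(0.2500 + 0.2275)/20] = 0.254.

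**Step 4: consequence for planning.** The number per arm for a later trial (two-sided 5%, 80% power, pooled-variance formula) is n = [1.960√(2m(1 − m)) + 0.842√(a(1 − a) + b(1 − b))]² / (a − b)², with m the mean of a and b.

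| q | Usual care | PediCARE | Difference (points) | 90% half-width (points) | n per arm, later trial |
|---|---|---|---|---|---|
| 0 | 50.0% | 35.0% | 15.0 | 25.4 | 170 |
| 10% | 55.0% | 41.5% | 13.5 | 25.7 | 214 |
| 20% | 60.0% | 48.0% | 12.0 | 25.7 | 270 |
| 30% | 65.0% | 54.5% | 10.5 | 25.4 | 342 |

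The loss is 1.5 to 4.5 points, against a half-width of about 25 points.

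**Step 5: one child.** A scheduled stay changes an arm's proportion only if the child has no other ED or ICU event. The expected shift from one such child is (1/20)(1 − p): 0.05 × 0.50 = 2.5 points in usual care and 0.05 × 0.65 = 3.25 points under PediCARE. The per-patient ICU count is different, because every scheduled stay enters it.

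**The case against.** The strongest case against has four parts.

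- **The size is unknown.** The documents show that surgery can occur in this cohort. They do not show that any enrolled child will have a scheduled ICU stay, or that post-operative ICU care is usual at either site. This stands, and the point must stay conditional.
- **The pilot cannot see it.** The endpoint is secondary and estimation-only, and the sampling error is several times the shrinkage. This also stands and limits the weight of the point. But sampling error falls as the trial grows, and the shrinkage does not.
- **All-cause ICU use is a defensible endpoint.** The plan speaks of utilization. If the next RCT keeps the same definition, the pilot's rates are the matching inputs. That is true, but that trial then pays for the shrinkage in sample size, as Step 4 shows. If it changes the definition, the pilot without a planned-status field cannot supply the right inputs.
- **The remedy trades an objective count for a judgement.** Section 9.2 says the study team is unblinded after randomization, and Section 9.1.3 has only 10% of records abstracted twice. Coding with knowledge of arm could bias the estimate either way. This is a real cost. A chart rule fixed in advance, with the all-ICU result still reported, answers it adequately.

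A reader might also infer that one or two extra surgical children in one arm would move the result by 5 to 10 points. The documents do not support that. Surgery need not lead to an ICU stay, and at the assumed risks the expected shift is 2.5 to 3.25 points per child with a scheduled stay. Chance imbalance between arms is also ordinary sampling variation, which the 90% interval is there to reflect, and not the shrinkage described here.

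**Conclusion.** The point holds as a conditional weakness in the endpoint definition. Every ICU stay counts, fewer is read as benefit, and the eligibility criteria admit children who may have planned surgery during the 6 months. If scheduled stays occur at a rate q that is equal in the arms and independent of other events, the risk difference is multiplied by (1 − q). Under the assumed risks this is a loss of 1.5 to 4.5 points out of 15 for q of 10% to 30%. With q = 0 there is no loss.

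Two stronger conclusions are tempting but go too far. The documents do not show that the estimate is in fact diluted, because they give no value for q. They also do not establish that the abstraction form lacks a planned-status item: the list is open-ended and the form is not included. What they do show is that no such item is named and that the endpoint definition would not use it.

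The primary feasibility endpoint is unaffected. The reason to act is the endpoint's stated role in planning the definitive trial.

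**What to change.** Add one abstraction field for each ICU stay, coded by a rule written before abstraction starts: scheduled if the chart documents ICU care as planned before the admission or procedure, otherwise unscheduled. In H2b, Section 8.2 and Section 11.0, define the event as an ED visit or an unscheduled ICU stay. Report the version with all ICU stays as a supporting line, for both the proportion and the per-patient counts.

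The cost is one field in at most 40 charts and a wording change in three places. A few stays will need a judgement. Because the team is unblinded, the rule must be fixed in advance and applied without reference to arm, and the all-ICU line serves as the check on that coding.
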